For any subject who leaves the study, the Investigator must complete the CRF up to the time of withdrawal, ascertain the reason for discontinuation, and perform the EOS procedures. All reasonable efforts must be made to contact subjects who fail to return for scheduled visits and to encourage them to comply with the procedure. All attempts to contact subjects either by phone, courier, and/or email must be clearly documented. In case of withdrawal of consent, the date of withdrawal and the reason for withdrawing consent if provided by the subject will be collected. No additional data will be collected from the time of withdrawal of consent.

In the case of premature voluntary withdrawal of a subject with the premature stop of treatment with Pylera®, the subject will be excluded from the study and will be monitored separately. For subjects who have halted treatment with Pylera® and have withdrawn due to a neurological AE indicative of bismuth encephalopathy, the subject will be followed up through a separate Pylera® Intensive Monitoring Program.

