9.2.2 Subjects who prematurely discontinue treatment with Pylera®

For any subject who prematurely discontinues treatment with Pylera®, the Investigator will perform the EOS procedures and will complete appropriate pages of the CRF. A diagnostic *H. pylori* test (breath test, biopsy, or other test) will be conducted at the discretion of the Investigator.

In case of withdrawal of consent, only the date of and the reason for withdrawing consent will be collected on the CRF. Otherwise, the Investigator will make all reasonable effort to complete as much as possible the following at the time of discontinuation.

#	Information to be collected
1	Vital sign measurements (pulse rate, blood pressure measured from the same arm throughout the study)
2	Record of any occurrence of AEs, change in concurrent medical conditions, use of adjunctive therapy/procedure, and intake of concomitant medication
3	Collect safety information via a phone call to the patient 30 ± 5 days after discontinuation (includes AEs, change in concurrent medical conditions, use of adjunctive therapy/procedures, and intake of concomitant medication).

4	A diagnostic H. pylori test (breath test, biopsy, or other test) at the discretion of the Investigator
---	--

All results of evaluation and observations, together with the reason for withdrawal from the study, will be recorded on the CRF.

For any subject who prematurely discontinues treatment with Pylera® due to a neurological AE indicative of bismuth encephalopathy, the subject will be followed up through a separate Pylera® Intensive Monitoring Program.

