10 ADVERSE EVENTS

Subjects receiving any investigational drug require careful observation. Any adverse event/concurrent illness experienced by a subject during any portion of the study must be described in detail and be fully evaluated by the Investigator. The Investigator is responsible for recording all adverse events observed or reported during the study from Inform Consent signature until date of completion/discontinuation, regardless of the drug-related assessment and/or clinical significance. Any pertinent information must be recorded in the CRF and additional comments describing the course and outcome of these events should be provided as appropriate.

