APPENDIX 3 – CENTRAL NERVOUS SYSTEM ADVERSE EVENTS OF INTEREST

Bismuth neurotoxicity is typically characterized by encephalopathy, which is defined as any degenerative or diffuse disease of the brain that alters brain structure or function.

In order to select the appropriate terms, the original Standardized MedDRA Query (MedDRA 15.1SMQ Noninfectious encephalopathy/delirium (20000133)) was revised to specifically address the bismuth encephalopathy and include signs and symptoms that are specific to this risk.

Preferred Terms (narrow scope): Encephalopathy, Toxic encephalopathy

Preferred Terms (broad scope):

Abnormal behavior;	apraxia; Gait disturbance;	changes; Mood altered;
Agitation; Agraphia; Alexia;	Generalised non-convulsive	Myoclonus; Paresis anal
Altered state of	epilepsy; Grand mal	sphincter; Partial seizures;
consciousness; Amnesia;	convulsion; Hallucination;	Partial seizures with
Anal sphincter atony;	Hallucination, auditory;	secondary generalization;
Apathy; Ataxia; Bladder	Hallucination, gustatory;	Personality change;
sphincter atony; Cerebellar	Hallucination, olfactory;	Personality disorder;
ataxia; Cerebellar syndrome;	Hallucination, synaesthetic;	Psychomotor seizures;
Clonic convulsion; Coma;	Hallucination, tactile;	Restlessness; Simple partial
Coma scale abnormal;	Hallucination, visual;	seizures; Sleep disorder;
Complex partial seizures;	Hallucinations, mixed;	Slow response to stimuli;
Confusional state;	Hypersomnia;	Sluggishness; Somnolence;
Convulsion; Convulsions	Hyporesponsive to stimuli;	Speech disorder; Stupor;
local; Coordination abnormal;	Illogical thinking	Thinking abnormal; Tonic
Delirium; Depressed level of	Incontinence ; Judgement	convulsion; Tremor;
consciousness; Disturbance in	impaired; Lethargy; Listless;	Unresponsive to stimuli;
attention; Dysarthria;	Loss of consciousness;	Urinary incontinence.
Dysgraphia; Dyspraxia;	Memory impairment; Mental	
Faecal incontinence; Gait	impairment; Mental status	

A “narrow” scope represents the condition of interest and a “broad” scope helps to identify all possible cases, including some that may prove to be of little or no interest on closer inspection. Thus, a “narrow” search yields “specificity” while the “broad” search yields “sensitivity.”

The presence of these events will be identified and assessed at the End of Treatment and End of Study visits only as the event would need to be treatment-emergent in order to be potentially associated with potential bismuth neurotoxicity.

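### The protocol contradicts itself on whether subjects who withdraw and stop Pylera early stay in the study data, and on how long early stoppers' adverse events are recorded

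*Protocol*

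**What the plan says.** **Section 4.6, first paragraph after the table.** This covers every leaver, whatever the reason: "the Investigator must complete the CRF up to the time of withdrawal, ascertain the reason for discontinuation, and perform the EOS procedures". If consent is withdrawn, only the date and any reason given are kept.

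**Section 4.6, next paragraph.** For voluntary withdrawal combined with an early stop of Pylera, "the subject will be excluded from the study and will be monitored separately". Withdrawals due to a neurological AE indicative of bismuth encephalopathy go to the Intensive Monitoring Program.

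**Section 9.2.2.** For any early stop, "the Investigator will perform the EOS procedures and will complete appropriate pages of the CRF". Unless consent is withdrawn, the investigator should also "complete as much as possible the following at the time of discontinuation": vital signs, AEs and medication, an *H. pylori* test at discretion, and a later contact, "Collect safety information via a phone call to the patient 30 ± 5 days after discontinuation". The CNS form is not on this list.

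**Section 10.** The investigator is responsible for "recording all adverse events observed or reported during the study from Inform Consent signature until date of completion/discontinuation".

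**Section 10.4.1.** AEs found at any follow-up contact, including by phone, go on the CRF's AE form.

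**Section 9.2.1, Appendix 1 and Appendix 3.** The CNS form belongs to the End of Treatment (EOT) and EOS visits. Appendix 3 adds: "The presence of these events will be identified and assessed at the End of Treatment and End of Study visits only".

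**Sections 11.7.1.3 and 11.7.1.4.** The Safety Population is every enrolled subject who consented. Safety is analysed on observed cases, without imputation.

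**The concern.** An AE is one of the listed reasons for discontinuation (section 4.6, criterion 3), so missing data after an early stop may well be related to safety. Premature withdrawal also counts as a major deviation (section 11.7.1.2). These subjects therefore leave the Per Protocol population, and the Safety Population is the only analysis set in which they count.

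If sites apply different rules, the amount of follow-up behind each AE percentage will depend on which sentence the site read. With observed-case analysis, an unrecorded AE counts as no AE while the subject stays in the denominator. If the subject is removed instead, the analysis set departs from its own definition. Either way the reported profile can look better than it was, in a study requested in order to observe real-life use, including poor compliance and misuse (section 1.2).

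**Working it through.** The plan states no figure on this point, so there is nothing to reproduce. The check compares the passages, followed by timing arithmetic and an illustration.

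**1. In or out of the study data?** The exclusion sentence in 4.6 takes the subject out. The paragraph before it and 9.2.2 keep the subject in (EOS procedures, CRF pages), and 11.7.1.3 keeps the subject in the Safety Population. The exclusion sentence cannot stand with the other three. The first paragraph of 4.6 and 9.2.2 do agree with each other, because the call can be read as an addition to the EOS procedures.

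**2. Until when are AEs recorded?** Section 10 sets the period as "from Inform Consent signature until date of completion/discontinuation". If discontinuation means stopping Pylera, an AE that starts later and is reported at the call lies outside the period, although 9.2.2 plans the call to collect AEs and 10.4.1 says AEs reported by phone are recorded. The 30-day extension in 10.4.3.1 covers only spontaneously reported serious AEs.

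**3. Timing of contacts.** For a completer, EOS is on Day 39:
- 39 − 11 = 28 days after EOT
- 39 − 10 = 29 days after a last dose on Day 10

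For a last dose on Day s, the call falls between Day s + 25 and Day s + 35:
- s = 1: Day 26 to 36
- s = 9: Day 34 to 44

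Under 9.2.2, general AEs are thus followed about as long as in completers. Under the exclusion sentence, or the literal cut-off in section 10, follow-up in the study data ends at discontinuation.

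**4. CNS assessment.** EOS procedures bring one CNS form (9.2.1, Appendix 1). Section 9.2.2 gives no date for them after an early stop. If they are done at discontinuation, the only later scheduled contact is the call, whose listed content has no CNS form, and Appendix 3 ties the structured check to EOT and EOS.

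**5. Illustration of size (assumed rates, none in the protocol).** Suppose 2% to 15% of 200 stop early (4 to 30 subjects), with any AE in 30% of the others and in 50% to 100% of early stoppers. As a worst case, suppose every AE of the early stoppers is lost.

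| Early stoppers | Full data | AEs lost, denominator 200 |
|---|---|---|
| 4 | (196 × 0.30 + 4 × 0.50 to 1.00)/200 = 30.4% to 31.4% | 58.8/200 = 29.4% |
| 30 | (170 × 0.30 + 30 × 0.50 to 1.00)/200 = 33.0% to 40.5% | 51/200 = 25.5% |

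If early stoppers are removed from the denominator as well, the result is 30%.

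For a rare event, losing one case turns 1/200 (two-sided 95% exact upper limit 2.75%) into 0/200, with limit 1 − 0.025^(1/200) = 1.83%. With 20 subjects also removed, it becomes 0/180, with limit 1 − 0.025^(1/180) = 2.03%.

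**The case against.** **CNS follow-up.** A reader might infer that early stoppers get no later CNS check. The protocol does not say that. EOS procedures are required for them and include the CNS form. Section 10.4.3.3 requires the neurological reporting form whenever Appendix 3 symptoms occur, without tying it to a visit, and early stops due to a neurological AE indicative of encephalopathy go to the Intensive Monitoring Program. What stands is narrower: the date of the EOS procedures is open, and no structured check is guaranteed after the day of stopping.

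**AE recording.** A reader might also infer that a site following section 10 records nothing after the stop date. Section 10.4.1 says otherwise for phone contacts and asks that AEs be followed to resolution where possible. The section 10 phrase can also mean leaving the study rather than stopping the drug. This shows that the passages need aligning, not that the data are certainly lost.

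**Scope.** The exclusion sentence covers only voluntary withdrawal together with an early stop, not everyone who stops Pylera. It might be meant for withdrawal of consent, where ending data collection is proper. But 4.6 handles that case in the preceding paragraph, and continued monitoring fits poorly with collecting no further data.

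**Impact.** Safety is descriptive, the primary objective is pharmacokinetic, and the link between bismuth concentration and neurological symptoms is also reported through the PSUR and the Intensive Monitoring Program. That limits the consequence. It does not repair this study's own safety tables.

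**Conclusion.** The contradiction is real and is in the current text. The exclusion sentence in 4.6 conflicts with the paragraph before it, with 9.2.2 and with the Safety Population. The section 10 cut-off sits badly with the planned call and with 10.4.1. Followed as written, either one would drop later AEs from an observed-case analysis and could make AE percentages too low.

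The size is unknown, because the protocol gives neither an early-stop rate nor an AE rate in such subjects. The illustration is an upper bound on assumed inputs: AEs before the stop, including one that caused it, fall within the section 10 period and should be on the CRF. The documents do not support a claim that CNS events would be systematically missed, or that an observed CNS rate would be some particular fraction of the true one. That would need late-event rates the protocol does not contain, and the failure of both the call and the symptom-triggered form.

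**What to change.** Reconcile sections 4.6, 9.2.2, 10, 10.4.1, 11.7.1.3 and Appendix 3 so that one consistent rule states:

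- whether subjects who withdraw and stop Pylera early stay in the study data and the Safety Population, with withdrawal of consent as the exception
- until when their AEs are recorded, so that events reported at the call already planned count in the safety tables
- when the EOS procedures, and with them the CNS assessment, take place after an early stop
- what the separate monitoring in 4.6 is, and whether AEs found there enter the study database

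Which follow-up rule is right is for the sponsor and investigators to decide. The statistical requirement is that there is only one and that the analysis set matches it. The cost is small: wording changes in a few sections and slightly more data recorded for a few subjects.

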5 STRATIFICATION AND RANDOMIZATION

As this is a single arm open-label study, no randomization will occur. No *a priori* stratification of subjects will be performed for this study.

	Page 24 of 96
	Protocol # : MA-PY-HpPK11-01

6 UNBLINDING

Not applicable.

7 ADMINISTRATIVE PROCEDURES AND ETHICAL CONSIDERATIONS

Aptalis Pharma US, Inc. ensures the following obligations and administrative aspects of the study have been discussed with Investigators. These are described below:

- The Investigator must acknowledge Aptalis Pharma US, Inc. has instituted a Quality Assurance program according to Good Clinical Practices (GCPs), International Conference on Harmonisation (ICH) Guidelines and applicable laws and regulations;
- The Investigator must agree to allow study monitoring activities throughout the conduct of the study;
- The Investigator must agree to the inspection of study-related records by regulatory agency and/or Aptalis Pharma US, Inc. or designate;
- The Investigator must adhere to the European Medicines Agency (EMA) principles in addition to any applicable or local requirements.
- The Investigator must document in the CRF, Pylera® treatment description and compliance: date of first dose, date and hour of last dose, premature discontinuation of Pylera®, and if the subject took all doses.

7.1 AUDITING PROCEDURES

Aptalis Pharma US, Inc. has instituted a Quality Assurance program to ensure all aspects of the study have been conducted according to Good Clinical Practices, ICH Guidelines and applicable laws and regulations. This may include but is not limited to an audit by Aptalis Pharma US, Inc. and/or regulatory agency representative (Health Protection and Food Branch at Health Canada, Food and Drug Administration [FDA] of United States of America, EMA of European Union, and any other health regulatory agencies) at any time. The Investigator must agree to the audit of study-related records by regulatory agency and/or Aptalis Pharma US, Inc. The Investigator must adhere to the following principles, in addition to any applicable or local requirements.

7.2 MEDICAL CARE

Subjects will be informed that their medical care will not be affected by their agreement or refusal to participate in this study, and that they are free to withdraw from the study at any time without prejudice to the clinician-subject relationship.

7.3 SUBJECT INFORMATION AND INFORMED CONSENT

Information will be provided to explain, in simple terms, the risks and benefits of the subject's participation in the study, the procedures involved, and other relevant details. Written Informed Consent must be obtained from the subject by the Investigator before the subject enters the study.

The Investigator must adopt a standardized approach for obtaining Informed Consent from each subject. The following items must be described fully to each subject prior to obtaining consent:

- A statement that the study involves research, an explanation of the purposes of the research and the expected duration of the subject's participation, a description of the procedures to be followed and identification of any procedures which are experimental;
- A description of any reasonable foreseeable risks or discomforts to the subject;
- A description of any benefits to the subject, which may reasonably be expected from the research;
- A disclosure of appropriate alternative procedures or courses of treatment, if any, which might be advantageous to the subject;
- A statement describing the extent, if any, to which confidentiality of records identifying the subject will be maintained and that notes the possibility that the sponsor and the worldwide regulatory agency will inspect the records;
- An explanation of whom to contact for answers to pertinent questions about the research and research subject's rights, and whom to contact in the event of a research-related injury to the subject;
- A statement that participation is voluntary, that refusal to participate will involve no penalty or loss of benefits to which the subject is otherwise entitled and that the subject may discontinue participation at any time without penalty or loss of benefits to which the subject is otherwise entitled;
- A statement that participation in the bio collection is voluntary and that the subject may request the destruction of his/her biological samples;
- Anticipated circumstance under which the subject's participation may be terminated by the Investigator without regard to the subject's consent;
- Any additional costs to the subject that may result from participation in the research;
- The consequences of a subject's decision to withdraw from the research and procedures for orderly termination of participation by the subject;
- A statement that significant new findings developed during the course of the research which may relate to the subject's willingness to continue participation will be provided to the subject;
- The approximate number of subjects involved in the study; and
- Any other country-specific and ICH/GCP requirements.

Should the Investigator decide to modify the Informed Consent document, the modified version must be approved by Aptalis Pharma US, Inc. prior to its submission to the Research Ethics Board (REB)/ Institutional Review Board (IRB)/ Independent Ethics Committee (IEC). Should the REB/IRB/IEC request modifications; the REB/IRB/IEC's version must be submitted to Aptalis Pharma US, Inc. prior to study initiation.

The original signed Informed Consent document should be maintained with the source documents. The subject should receive a copy of the signed Informed Consent document. All signed and dated Informed Consent documents will be inspected by the Aptalis Pharma US, Inc. Clinical Research Associate (CRA).

7.4 ETHICS COMMITTEE REVIEW

The protocol and the Informed Consent document to be used in this study must be submitted to the Investigator's appropriate REB/IRB/IEC for approval. Written documentation of approval of the protocol, any protocol amendment(s) and the Informed Consent must be provided to the sponsor before starting the study. When necessary, an extension or renewal of the REB/IRB/IEC approval must be obtained and also forwarded to Aptalis Pharma US, Inc.

Upon approval and before study start, the following REB, IRB or IEC Approval Documentation must be sent to Aptalis Pharma US, Inc.:

- A letter documenting the REB, IRB or IEC approval of the protocol (indicating its title and number) and the Informed Consent document.
- A letter documenting the REB, IRB, or IEC approval of amendment(s) to the protocol (indicating its title and number) and/or the Informed Consent Form, if applicable.
- A list of the REB, IRB or IEC members, their representative capacity, and their affiliation.

The ICH Guidelines for GCP specify the committee should include persons of varying backgrounds (including peers of the responsible Investigator and lay people) and must exclude the responsible Investigator as a voting member.

7.5 STANDARDS

The study will be conducted according to the principles of the Declaration of Helsinki (Seoul, October 2008), and the ICH Guidelines for Good Clinical Practice. The Sponsor will ensure the study complies with all local, federal or country regulatory requirements as applicable.

7.6 CONFIDENTIALITY

Subjects will only be identified with a subject number. Their names will not be disclosed in any publication or presentation of results.

7.7 PROTOCOL ADHERENCE

Subjects who fail to adhere to protocol will be assessed on whether or not the lack of adherence was due to AEs.

The Investigator should make every effort to ensure that visits occur at the appropriate intervals. The reason for any deviation in the visit schedule must be documented in the CRF.

7.8 PROTOCOL AMENDMENTS AND OTHER CHANGES IN STUDY CONDUCT

Any substantial changes, other than strictly administrative changes that do not affect patient management, patient safety, clinical procedures, or outcomes assessment, will be made as formal amendments to the protocol and will be submitted to each participating site for appropriate review by an IRB, IEC, or a REB, and to regulatory authorities.

Any change or addition to this protocol requires a written protocol amendment that must be approved by Aptalis Pharma US, Inc. and the Investigator before implementation. Amendments significantly affecting the safety of subjects, the scope of the investigation, or the scientific quality of the study, require additional approval by the IRB/IEC/REB of all centers, and, in some countries, by the regulatory authority. A copy of the written approval of the IRB/IEC/REB, which becomes part of the protocol, must be given to the Aptalis Pharma US, Inc. CRA.

These are examples of amendments requiring such approval:

- Any increase in drug dosage or duration of exposure of human subjects to the drug beyond that in the current protocol;
- Any significant increase in the number of human subjects under study;
- Any significant change in the design of the protocol (such as the addition or dropping of a control group);
- Addition or deletion of a test procedure for safety monitoring
- An increase in the number of invasive procedures to which subjects are exposed

These requirements for approval should in no way prevent any immediate action from being taken by the Investigator or by Aptalis Pharma US, Inc. in the interests of preserving the safety of all subjects included in the trial. If an immediate change to the protocol is felt to be necessary by the Investigator and is implemented by him/her for safety reasons Aptalis Pharma US, Inc. should be notified and the IRB/IEC/REB at the center should be informed within 10 working days. Amendments affecting only administrative aspects of the study do not require formal protocol amendments or IRB/IEC/REB approval but the IRB/IEC/REB of each center must be kept informed of such administrative changes.

An example of an administrative change not requiring formal protocol amendments and IRB/IEC/REB approval that can be treated as administrative amendments is as follows:

- Changes in the staff used to monitor trials (e.g., Aptalis Pharma US, Inc. staff versus Academic Research Organization (ARO) staff)

	Page 29 of 96
	Protocol # : MA-PY-HpPK11-01

Changes in study conduct as defined in this protocol are not permitted. Any planned deviation from the specific requirements of the protocol must be discussed in advance with Aptalis Pharma US, Inc. and will require prior approval. Any unforeseen changes in study conduct will be recorded in the clinical study report. Please see section 11.6 for additional information on protocol deviations.

